Statistical Analysis Plan (SAP)

Study Title	Effects of Heart Rate Oscillations During Meditation on Plasma Biomarkers of Alzheimer's Disease
Principal Investigator	[name] Professor of Gerontology, Psychology and Biomedical Engineering University of Southern California Los Angeles, California, USA
Protocol Identification Number	UP-23-00373
ClinicalTrials.gov Identifier	NCT06210035
Author	[name] Research Associate [name] of Southern California Los Angeles, California, USA
Version	Draft 1.0
IRB Approval Date	5/25/2023

1. Objectives and hypotheses

The aim of the study was to examine how two types of meditation practices (with or without slow breathing) affect plasma A β levels of compared with a no-intervention control group. In addition, we examined the effects of the two types of meditation practices on emotional well-being relative to the control group.

We predicted that meditation with slow breathing would increase heart rate oscillations during practice, leading to greater reductions in plasma A β levels relative to the other conditions. In addition, we hypothesized that both meditation practices would improve emotional well-being compared with the control condition.

2. Sample Size & Power consideration

For plasma A β , we estimated reliability using correlations between pre- and post-intervention time points in the HRV-ER trial. Effect sizes were derived from the pre-post difference in the younger adult slow-paced breathing group of HRV-ER. We powered the study to detect small-to-medium effect sizes ($f = 0.2$) with a 0.459 correlation among repeated measures, aiming for 80% power at $\alpha = .05$. Based on these parameters, a total sample size of $N = 72$ (with two assessments) was required. Based on the HRV-ER study, we estimated a 12% dropout rate ($72 \times 12\% \approx 9$). Thus, we planned on a total enrollment of $N = 81$ ($72+9$) to achieve a final $N = 72$ for analyses. Ultimately, 89 participants completed the study.

3. Outcome Measures and Analyses

We examined condition differences in intervention-related change in the following outcome measures. The average time between pre- and post-intervention assessments was one week.

Primary outcome measures

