- **Change in plasma amyloid beta levels:** We computed an aggregate score based on plasma A β 40 and A β 42 levels (pg/mL), calculated as the average of their Z-scores. Higher values on this composite measure are associated with greater risk of Alzheimer's disease. We conducted a 2 (time: pre, post) \times 3 (condition: meditation with slow breathing, meditation without slow breathing, no intervention control) ANOVA to test for a time \times condition interaction in plasma A β levels, assessing group differences in change over time.
- **Change in plasma Ab42/40 ratio:** We conducted a time X condition ANOVA with plasma Ab42/40 ratio scores as the dependent variable (to assess group differences in change). The ratio was calculated by dividing the plasma Ab42 concentration (pg/ml) by the plasma Ab40 concentration (pg/ml).

Secondary outcome measures

- **Change in plasma pTau-181/tau ratio:** We conducted a time X condition ANOVA with plasma pTau-181/total Tau ratio scores as the dependent variable (to assess

group differences in change). The ratio was calculated by dividing the plasma pTau-181 concentration (pg/ml) by the plasma total Tau concentration (pg/ml).

- **Change in emotional well-being:** We conducted a time X condition ANOVA with emotional well-being as the dependent variable (to assess group differences in change). Emotional well-being was measured by the Profile of Mood States (POMS), which consists of 40 items that are rated on a 5-point scale ranging from "0=not at all" to "4=extremely. Total Mood Disturbance (TMD) was calculated by summing the totals for the negative items and then subtracting the totals for the positive items. A constant (i.e., 100) was added to the TMD formula to eliminate negative scores. Higher scores indicate more negative mood states. The scores range from 56 and 216.

Safety outcomes

Three non-serious adverse events were reported and subsequently resolved.

4. Populations and subgroups to be analyzed

Population analyzed is composed by all randomized subjects who completed assessments and whose data quality was sufficient for data analysis.

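### Two primary outcomes and no decision rule: if each is tested at .05 and either counts, the chance of a false-positive primary interaction is between 5% and 10%

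*SAP*

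**What the plan says.** SAP section 3 lists two items under its primary heading. The first is a composite of Aβ40 and Aβ42, "calculated as the average of their Z-scores", analysed by a 2 (time) × 3 (condition) ANOVA whose interaction is described as "assessing group differences in change over time". The second is the Aβ42/40 ratio: "We conducted a time X condition ANOVA with plasma Ab42/40 ratio scores as the dependent variable". Both tests are omnibus and have no direction.

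The only significance level in either document is a planning input in SAP section 2, "aiming for 80% power at" .05. That section is written for plasma Aβ generally and does not say which primary outcome was powered. On the source of the effect it says "Effect sizes were derived from the pre-post difference in the younger adult slow-paced breathing group of HRV-ER".

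The only amyloid hypothesis, in SAP section 1, has slow breathing "leading to greater reductions in plasma" Aβ levels. The protocol's Research Objectives also speak only of Aβ levels. The ratio appears nowhere outside SAP section 3.

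The SAP was written after the trial ended: "Ultimately, 89 participants completed the study". Section 4 limits the analysis to randomised subjects who completed assessments and "whose data quality was sufficient for data analysis".

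**The concern.** With two primary tests and no rule linking them, the plan does not define a positive primary result. A significant interaction on the composite alone, on the ratio alone, or on both could each be reported as one, and the error rates of these readings differ widely.

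The two outcomes are not interchangeable. If both peptides change by the same factor c, the ratio becomes (c × Aβ42)/(c × Aβ40), which is unchanged, while the composite moves. One outcome can therefore be positive and the other flat.

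Because the SAP already reports the completed sample, a reader of these documents cannot tell whether any priority between the outcomes was set before the results were known.

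**Working it through.** **Inputs.** From SAP section 2: f = 0.2, correlation among repeated measures ρ = 0.459, α = .05, target power 80%, N = 72 required, 89 completers. From SAP section 3: m = 2 time points, k = 3 conditions, two primary outcomes. Assumed: equal arms (no allocation ratio is stated), and a range of values for r, the correlation between the two change scores, which the documents do not give.

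**1. The plan's own N.** For one interaction test with noncentral F on 2 and N − 3 degrees of freedom, take λ = f² × m × (N − k)/(1 − ρ).
- N = 72: λ = 0.04 × 2 × 69/0.541 = 10.20, power 80.6%.
- N = 71: power 79.9%.

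This convention gives the SAP's 72 exactly. The alternative, λ = f² × m × N/(1 − ρ), gives λ = 10.65 and power 82.3% at N = 72, and first reaches 80% at N = 69. Under either convention, 72 is sized for a single test at the full .05. Figures from the alternative follow in brackets.

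**2. False positives, both outcomes null, each tested at .05.**
- Either counts, independent: 1 − 0.95² = 0.0975.
- Either counts, any dependence: at most 0.05 + 0.05 = 0.10.
- Lower limit, when the two tests coincide: 0.05.

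Simulation of two correlated change scores in three arms of 24, with F(2, 69):

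| r | at least one p ≤ .05 | both p ≤ .05 |
|---|---|---|
| 0 | 9.8% | 0.2% |
| 0.5 | 9.2% | 0.8% |
| 0.7 | 8.5% | 1.5% |
| 0.9 | 7.1% | 2.8% |
| 0.99 | 5.7% | not run |

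If both are required, the chance of a false claim cannot exceed 5%, because at least one true null must be rejected at .05.

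**3. Effect of Holm on false positives.** The smaller p is compared with .025 and, only if that is significant, the larger with .05. In the same simulation the chance of at least one false positive is 5.0% at r = 0, 4.7% at r = 0.5 and 3.7% at r = 0.9.

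**4. Power under Holm, for an outcome with f = 0.2.**
- Single test at .025, N = 72: 71.5% (73.7%).
- Only one outcome responds, N = 72, r = 0: 0.715 + (0.806 − 0.715) × 0.025 = 0.717, about 72% (about 74%).
- Both respond, N = 72, r from 0 to 0.5: about 77–78% per outcome (79–80%).
- N = 89: from 89.1% at .05 to 82.6% at .025 (90.1% to 84.1%). The .025 figure is the floor under Holm within each convention.
- Smallest N for 80% at .025: 85 (82). So 89 − 85 = 4 completers (89 − 82 = 7) could be excluded for data quality before the floor drops below 80%.

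**The case against.** The strongest reply is that the composite is evidently the lead outcome. It is listed first, and the protocol objective and the only amyloid hypothesis both concern Aβ levels. That is a fair hint of priority. But section 3 gives the ratio the same primary status, and list order is not a testing rule.

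A second reply is that the SAP never says either outcome alone suffices, and that two measures built from the same two peptides are unlikely to be independent. Both points stand. They are why the 9.75% is conditional and why the range runs down to 5%. They do not supply the missing rule.

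A third is that Holm is partly a preference and costs about 9 points of power at N = 72 in the case the hypothesis describes, where only Aβ levels respond. That cost is real. Holm is still the safer default, because it needs no knowledge of r and no proof of when an order was chosen.

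A fourth is that the trial is complete, so no rule added now can prespecify anything. That is correct: the gain is a limit on what is claimed.

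A reader might also argue that the directional hypothesis makes the relevant error rate much lower. The documents do not support a figure for this. The planned tests are omnibus, and no favourable direction is stated for the ratio; section 3 links higher values to risk for the composite only.

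**Conclusion.** The gap is real and should be fixed. Two primary outcomes are tested separately, with no order, alpha split or one-or-both rule. If each is tested at .05 and either counts, the false-positive rate for the primary family is 9.75% under independence, at most 10%, and between 5% and 10% according to a correlation the documents do not give. If both are needed, it is at most 5%.

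This rests on two assumptions: that .05 applies to each test, which is inferred from the power section, and that either outcome would count. It covers only the two primary interaction tests, not comparisons between pairs of conditions or secondary outcomes.

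A reader might infer that the trial actually runs a 10% error rate, or that the ratio was made primary after the results were seen. The documents support neither. They do not state an either-counts rule, and they show only that the SAP text was written after completion, not when the outcomes were chosen.

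**What to change.** Add to SAP section 3: *The two primary outcomes are tested with the Holm procedure at a family-wise level of .05: the smaller p-value is compared with .025 and, if significant, the larger with .05. Unadjusted and Holm-adjusted p-values are reported for both.*

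State when the rule was adopted, and label it post hoc unless an earlier record shows otherwise. A fixed sequence with the composite first, which would keep the full .05 for the composite, should be used only if that order is documented to predate the results.

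In SAP section 2, state that the 80% power is for a single test at .05, and have the sponsor say which outcome it refers to.

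The change takes a few sentences, with no new data and no rerun of the ANOVAs. The costs are:
- If only one outcome responds, power at the planned N = 72 falls below the 80% target. If both respond, the loss at N = 72 is about 2 to 4 points per outcome across the two conventions.
- With 89 completers power stays above 80%, but 89 is an upper limit on the analysed number, and under the convention that matches the SAP only 4 exclusions are affordable.
- If the smaller p-value lies between .025 and .05, neither outcome can be called positive.
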